β_{1j} Month + β_{2j} Imp + β_{3j} Month * Imp + e_{ij} , where (1) Logit(Y_{ij}) denotes the logit (or log-odds) of receiving bundle performance for the i^{th} ICU-day of the j^{th} patient; (2) Month is the month indicator of the study period (a total of 20 months coded as -5 to 0 for pre-implementation period and 1 to 14 for implementation period); and (3) Imp denotes an indicator variable coded as 0 for pre-implementation period and 1 for the implementation period. Therefore, Logit(Y_{ij}) is modeled as a linear function of $\beta_{0j} + \beta_{1j}$ Month for the pre-implementation period and $(\beta_{0j} + \beta_{2j}) + (\beta_{1j} + \beta_{3j})$ Month for the implementation period. β_{2j} and β_{3j} are the estimates of level and slope changes due to the intervention implementation. A significant level change (β_{2j}) indicates an immediate change in the level of bundle performance at the initiation of intervention implementation. A significant slope change (β_{3j}) indicates different trends over time during the pre- vs. post-implementation periods. Under the multilevel modeling framework, level-2 models will fit β_{0j} , β_{1j} , β_{2j} , and β_{3j} each as a linear function of fixed-effects of patient characteristics and patient-specific random effects. The patient-specific random terms allow for adjustment of within-patient clustering of ICU-days. Take patient gender as an example. From the combined multilevel segmented logistic regression model, we will (1) estimate the overall trends during the pre- and implementation periods (solid black lines); (2) derive fixed-effect estimates by patient characteristics (Figure 4, long dashed line and short dashed line for each gender); (3) test the significance of hypothesized subgroup differences (e.g., older age, obese, and non-English speaking) in the these estimates; and (4) include patient-specific random terms to allow for variability by patients (patient-specific lines not shown in Figure 4). The model can be simplified if supported by the preliminary results. For example, if the initial analyses for an outcome (e.g., element E performance) suggest that (1) there are no significant level change and slope change for both male and female patients and (2) the overall increasing trend over time does not differ by patient gender, we can reduce the model to a parsimonious form using multilevel logistic regression to model the probability of having an outcome as a function of fixed effect of patient gender, fixed effect of time, and patient-specific random effects. We can also further extend the model to (1) include multiple patient characteristics simultaneously in the model to generate multivariable adjusted estimates, (2) perform curve fitting for linear or non-linear trend, and (3) adjust for additional clustering (e.g., within-organization clustering). The above desried multilevel segmented logistic regression approach will be applied to analyzing complete and element bundle performance measures. For proportional bundle performance, we will use multilevel segmented Poisson regression instead.

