Data Analysis. The overall analytic strategy for Aim 2 will be the same as described for Aim 1. That is, using multilevel segmented logistic regression modeling for complete and element bundle performance and multilevel segmented Poisson regression for proportional performance. First, we will examine the variation across ICUs in bundle performance by adding ICU-specific random effects to the model. All significant patient-level characteristics from Aim 1 will remain in the model as covariates so that ICU-level estimates are risk-adjusted for patient case mix. From the model, we can (1) quantify the degree of ICU variation using the intra-class correlation (ICC); (2) derive the ICU-specific adjusted rates of bundle performance at the last month of implementation and examine their distribution (mean, variance, median, interquartile range, and range); and (3) rank the ICU-specific adjusted rates from low to high and identify the top 5 and bottom 5 ICUs with best and worst adjusted performance rates. Next, we will estimate the effects of organizational characteristic on bundle adoption by adding them as fixed effects to the model. Organizational survey at the post-implementation period will be estimated as fixed effects to model the level change (β_{2j}) and slope change (β_{3j}). While data from the pre-implementation period will be estimated as fixed effects to model pre-implementation level (β_{0j}), pre-implementation slope (β_{1j}), post-implementation level change (β_{2j}), and slope change (β_{3j}) (see **Data Analysis section for Aim 1**). Again, multilevel clustering (within-patient clustering of ICU days and within-ICU clustering of patients) will be adjusted in the model using random effects terms. As the provider-level data can be linked to specific ICUs, but not linkable to specific patient and patient ICU days, we will use multilevel modeling (level-1: time-point [pre- and post-survey], level-2: provider; level-3: ICU) to model the fixed effect of time, provider-level assessments (AITCS, HWEA,^{136,137} and ICU Care and Perceptions surveys), and their interactions on ICU-level adjusted performance rates. From the model, we can derive contrast estimates on the effect of change in

provider-level assessments on ICU-level bundle adoption. We will also extend the model to adjust for ICU-within-organization clustering.

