Methods. The first section of the survey will provide participants the name and brief description of each of the 73 implementation strategies recommended in the ERIC project. Participants will be asked to think about the strategies they used during the course of the ICU Liberation Collaborative to increase their units' adoption of the ABCDEF bundle. Participants will then be asked to review each ERIC implementation strategy and to select "yes or no" as to whether they used the strategy during the time they spent in the ICU Liberation Collaborative. If "no" is selected, participants will be directed to the next question. If "yes" is selected, the participants will then be asked to rate, on a 5-point Likert scale, how (1) helpful, (2) acceptable, (3) feasible, and (4) costly it was to use the strategy. In the next section of the survey, participants will be provided the opportunity to report any additional implementation strategies they used to foster ABCDEF bundle adoption during their time in the ICU Liberation Collaborative that were not included in Section 1. If participants think of any additional strategies, they will be asked to provide the name and a short definition of the strategy. They will then be asked to rate, on a 5-point Likert scale, how (1) helpful, (2) acceptable, (3) feasible, and (4) costly it was to use the strategy. If participants feel the list of terms in Section 1 was adequately comprehensive, they will be instructed to leave this section blank. The final section of this survey will collect basic information regarding site location and type of professionals who assisted in survey completion. Because we are requesting the engagement of multiple stakeholders, we anticipate that the time necessary to complete the survey may vary by site. We estimate it will take approximately **20 minutes** for an individual to complete the survey and approximately **40-50 minutes** for team gathering and joint completion of the survey.

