Data Analysis. Survey. Quantitative data of the survey will be analyzed using the same approach as in Aim 2 for organization-level characteristics. In short, implementation strategies will be estimated as fixed effects to model the level change and slope change using multilevel segmented logistic regression modeling with patient-, hospital-, and organization-specific random effects to adjust for multilevel clustering effects. **Concept Mapping.** The study's planned minimum enrollment of 40 is above the recommended sample size for concept mapping (≥ 15).¹⁴⁶ In this stage, multidimensional scaling and hierarchical cluster analysis will be used to characterize how implementation terms were clustered by the healthcare provider panelists, providing the opportunity to quantitatively characterize the categories of terms developed by the providers in terms of how they were rated on key dimensions. Final data analyses will include visual summaries of data, including weighted and unweighted cluster maps, ladder graphs, and go-zone graphs, all specific tools from the web platform used for this analysis.¹⁴¹⁻¹⁴³ As described above cluster maps provide a visual representation of the relatedness of concepts, and weighted cluster maps are used to depict how concepts within a cluster were rated on key dimensions (e.g., importance). Ladder graphs provide a visual representation of the relationship between dimensions of a concept (e.g., importance and feasibility, importance and changeability). Go-zone graphs are useful for illustrating the concepts that are most actionable (e.g., high importance and high feasibility) and which concepts are less actionable (low importance and low feasibility). Bridge values (i.e., quantitative characterizations of how closely individual concepts within a cluster are related) will also be reported. **Expert Panel.** Following the interactive web-based discussion, the investigator team will review the notes, summarize the main points of discussion and include the list of recommendations that emerged from the Expert Panel discussion. These findings and recommendations will be circulated to the participants for feedback and validation.

Aim 4: Identify and describe the micro-decisions (e.g., resource allocation, patient participation, preferences, agreement) involved in implementing SATs, SBTs, and early mobility/exercise in everyday care.

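### Aim 3 places each strategy on the level change and slope change only, so any baseline difference between users and non-users is read as a strategy effect

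*Combined protocol and SAP*

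**What the plan says.** Aim 3, Data Analysis (Survey), states that the strategy data will be "analyzed using the same approach as in Aim 2 for organization-level characteristics". It then summarises that approach: "implementation strategies will be estimated as fixed effects to model the level change and slope change using multilevel segmented logistic regression modeling". On clustering, the summary has the model fitted "with patient-, hospital-, and organization-specific random effects to adjust for multilevel clustering effects".

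Aim 2, Data Analysis, has two routes for organizational data. For the later survey, "Organizational survey at the post-implementation period will be estimated as fixed effects to model the level change", together with the slope change. For the earlier survey, "data from the pre-implementation period will be estimated as fixed effects to model pre-implementation level", and also the pre-implementation slope, the level change and the slope change.

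The strategy item asks sites "whether they used the strategy during the time they spent in the ICU Liberation Collaborative" (Aim 3, Implementation Methods Survey, Methods). It is therefore implementation-period information. That timing and the Aim 3 summary sentence both point to the first route, with two coefficients. In Aim 1, by contrast, all four coefficients are modelled on patient characteristics. Nothing in Aims 2 or 3 checks whether users and non-users of a strategy had the same baseline level or trend.

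**The concern.** In the segmented model the slope change is the implementation-period slope minus the pre-implementation slope. A strategy can be credited with a difference in that change only if users and non-users may each have their own baseline. Leaving out the strategy main effect and its interaction with month fixes the two baselines to be equal. Under randomisation that restriction would be defensible. Here sites selected their own strategies, and the plan itself notes that they began with different experience of the bundle components.

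This model is Aim 3's regression test of which strategies go with greater adoption. The Approach section says the results will inform strategies for a later cluster randomized trial. The same restriction applies to each of the 73 listed strategies.

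**Working it through.** **Algebra.** Aim 1 gives logit(Y) = β0 + β1·Month + β2·Imp + β3·Month·Imp, with "a total of 20 months coded as -5 to 0 for pre-implementation period and 1 to 14 for implementation period". Let S = 1 for an ICU that used the strategy, and add γ2·S·Imp + γ3·S·Month·Imp, as Aim 3 states.
- Before implementation, both groups have the line β0 + β1·Month.
- During implementation, the slope is β1 + β3 for non-users and β1 + β3 + γ3 for users.

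So γ3 is the users' implementation slope minus the non-users' implementation slope. The difference in slope change is that quantity minus the baseline slope difference d1. If there is no true effect and d1 simply continues, γ3 = d1.

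**The plan's own figures.** Aim 2, Sample Size/Power Analysis, gives detectable odds ratios of 1.80 (level change) and 2.96 (slope change) at 80% power, with strategy use split 20:80. The implied standard errors are ln(1.80)/2.80 = 0.21 and ln(2.96)/2.80 = 0.39. They cannot be reproduced, because the simulation's random effects and model terms are not stated. Across the variants tried for the model as written, the detectable odds ratio was 1.23–2.88 for level change and 1.02–1.14 per month for slope change. None came near 2.96. With incomplete inputs, that does not show the figure to be wrong.

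**Inputs.**
- From the documents: 68 ICUs; 20 months; 5 patients per ICU-month at baseline and 15 afterwards; 3.3 days per patient; within-patient correlation 0.5; ICU correlation 0.3 (Aim 2) or 0.6 (Aim 1 power).
- User ICUs: 0.2 × 68 = 13.6, taken as 14.
- Assumed: outcome rate 10% (5% as a check) and the ICU random-effect terms shown in the table.

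**Method.** Generalised least squares on ICU-month logits.
- Design effect: 1 + (3.3 − 1) × 0.5 = 2.15.
- Variance per ICU-month: 2.15/(n × 3.3 × p(1 − p)). At p = 0.10 this is 1.45 for n = 5 and 0.48 for n = 15.
- ICU intercept variance: 3.29 × ICC/(1 − ICC), which is 1.41 at 0.3 and 4.94 at 0.6.
- Rejection probability: Φ(b/SE − 1.96) + Φ(−b/SE − 1.96).

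**Results for the model as written, with no true strategy effect.** The two middle columns use d1 = 0.10 log-odds per month. The fourth column is the share of a baseline level difference that appears as level change.

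| ICU terms | False slope change | False level change | Level share | Reject at d1 = 0.03 | Reject at d1 = 0.02 |
|---|---|---|---|---|---|
| Intercept, ICC 0.3 | 0.100 | 0.213 | 15% | 58% | 30% |
| Intercept, ICC 0.6 | 0.100 | 0.238 | 5% | 58% | 30% |
| None | 0.100 | 0.000 | 100% | 58% | 30% |
| ICC 0.3 + slope SD 0.05 | 0.096 | 0.205 | 15% | 30% | 16% |
| ICC 0.3 + slope SD 0.10 | 0.086 | 0.184 | 17% | 13% | 9% |
| Random terms on all four (slope SDs 0.10, level-change SD 0.5) | 0.086 | 0.184 | 17% | 9% | 7% |
| ICC 0.3 + AR(1) 0.5 month effects, SD 0.5 | 0.101 | 0.192 | 18% | 33% | 17% |
| Intercept, ICC 0.3, rate 5% | 0.100 | 0.189 | 25% | 35% | 18% |

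Example, first row: SE 0.0138, 0.03/0.0138 = 2.17, Φ(2.17 − 1.96) = 0.58. A second set of calculations, with other probability paths and random-effect sizes, gave 72–97% transfer of the slope difference under ICU random slopes and a level share of up to 46% with ICU random effects.

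**With S and S·Month added.** Both false effects are zero in every row. In the first row the standard errors rise from 0.180 to 0.286 (level) and from 0.0138 to 0.0874 (slope, 6.3 times). With slope SD 0.10 the slope standard error rises from 0.031 to 0.087 (2.8 times).

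**Simulation check** (binomial data, 400 runs per setting, ICU-clustered standard errors, ICU intercept SD 0.5). With no baseline difference, the model as written rejected in 5–6% of runs. A baseline slope ratio of 1.05 per month gave a false slope-change odds ratio of 1.05, significant in 92%. With the two baseline terms added, the odds ratio was 0.99 and rejection was 8–9%, against 7.5% for that model with no baseline difference.

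**The case against.** *The sentence is only a summary.* It follows a pointer to Aim 2, which in turn points to Aim 1, where all four coefficients are modelled. The authors may intend the same here. But Aim 2 explicitly separates the two routes, and strategy use belongs to the later period. The written rule is the restricted one, and at the least it needs clarifying.

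*Random effects will deal with it.* They absorb much of a level difference but little of a slope difference. They do change the false-positive rate greatly. A reader might take the 58% and 30% in the first row as the plan's error rates. The documents do not support that: those rates assume ICU intercepts only and a 10% outcome rate, and the plan does not say whether the hospital effects include slopes. If the standard error were the 0.39 implied by the plan's power statement, a 0.03 difference would reject about 5% of the time.

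*The bias makes strategies look effective.* A reader might infer that motivated, already improving ICUs used more strategies. No section links strategy use to baseline trend. Struggling ICUs might have used more, which would reverse the sign. For complete bundle performance, Preliminary Data reports a baseline below 4% with little trend, which leaves limited room for a difference as large as 0.10 per month. Other measures did move: element D rose by 0.05 in probability per month before implementation, and proportional performance was already rising.

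*Aim 2 has the same fault.* This is not established. If earlier- and later-survey terms share one model, stable characteristics already have baseline terms. The text does not say whether they do.

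**Conclusion.** The concern holds as a defect in the stated Aim 3 model. As written, the strategy slope-change effect is a contrast of implementation-period slopes. If strategy use is associated with baseline trend, nearly all of that trend difference is credited to the strategy: 86–100% here, and as little as 72% in the second set of calculations. A baseline level difference passes in part, or wholly if there is no ICU random effect. For a 0.03 per month baseline slope difference, the false-positive rate runs from about 13% to 58% over most variants, and is 9% if random terms sit on all four coefficients.

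This is conditional. The documents neither show nor rule out baseline differences between users and non-users, and they give no direction. If there are none, the model as written keeps close to its nominal error rate. The sizes rest on the assumed outcome rates and ICU variance terms. The algebra does not.

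**What to change.** 1. In Aim 3, Data Analysis, enter each strategy on the pre-implementation level, pre-implementation slope, level change and slope change. Interpret only the last two as strategy effects.
2. In Aim 2, Data Analysis, do the same for a later-survey characteristic wherever the model does not already carry the matching earlier-survey term on the baseline level and slope. State whether the two surveys share a model.
3. State whether the ICU or hospital random effects include slopes and change terms.
4. If the implementation-period slope contrast is wanted for its precision, report it under that name.
5. Re-simulate the detectable odds ratios of 1.80 and 2.96 under the corrected model.

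The change uses data already collected and adds two terms per strategy. The cost is precision, because the baseline has only 5 patients per ICU-month. At a 10% rate the level-change standard error goes from about 0.18 to 0.29, and the slope-change standard error from about 0.014 to 0.087 per month. At 5%, with no ICU random effects, the second set of calculations gave increases from 0.168 to 0.408 and from 0.020 to 0.125. Across its variants, the detectable odds ratio under the corrected model was 1.65–4.24 for level change and 1.16–1.54 per month for slope change. The corrected model's rejection rate of 7.5–9% in simulation, with only 14 user ICUs, suggests that the re-simulation should also check the type I error.

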Our preliminary data also show that collaborative participation resulted in significant but highly variable ABCDEF bundle adoption. Our next goal was to determine if collaborative participation led to increased bundle adoption. We were interested in exploring if some sites were "better" ABCDEF bundle adopters than others. The presence of a substantial amount of variability in our data would present us the opportunity to learn both from high- and low-bundle-performing sites. We calculated monthly rates of complete bundle performance, proportional bundle performance, and element-specific performance for the 17,258 patients across 49,109 full ICU days. We used segmented regression analysis for interrupted time series data to model the linear trend of bundle performance rates as a function of time for each segment (1-6 months pre-Collaborative involvement and 7-20 months during the Collaborative).

Complete bundle performance levels were low in the baseline (pre-Collaborative) period (i.e., < 4%). Complete bundle performance increased 2.0% (SE = 0.9%, $P = 0.057$) immediately after joining the Collaborative, and each month was associated with 0.6% greater increase (SE = 0.2%, $P = 0.038$) in complete bundle performance rates, compared to a relatively flat trend in the pre-Collaborative period. Proportional bundle performance rates also significantly increased by 3.8% (SE = 1.6%, $P = 0.026$) immediately after joining the Collaborative, then increased monthly at the same speed as the trend in the pre-Collaborative period (2%, SE = 0.4%, $P = 0.57$).

Bundle performance was highly variable among ICUs and across individual bundle elements; interquartile ranges of > 20% existed for all performance measures. (**Figure 1**) Elements A, C, D, and F were performed on average $\geq 70\%$ of the time at the end of the Collaborative:

Figure 1. Variation among ICUs in Unadjusted ABCDEF Bundle Performance Rates

adoption of elements B1, B2, and E (SATs, SBTs, and early mobility) proved far more challenging. For example, at the end of the Collaborative, an average $\leq 40\%$ of patients participated in early mobility and less than half of patients requiring MV received a daily SBT. Although overall performance was relatively poor, there were indeed some very good bundle performers.

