
Power analysis. We used the simulated-based power calculation method by Zhang et al.¹³³ for interrupted time series analysis to conduct power analysis for Aim 1. With the expected ~49,000 ICU-days of ~15,000 patients in 68 ICUs, we generated 1,000 simulations with various patient subgroup distributions and proportion of ICU days with bundle performance during the pre-implementation and implementation periods. Our preliminary analyses of the pre-implementation period data suggest that the probability of bundle performance ranged from 0.05 (for complete bundle performance) to 0.60 (for performance of element A) at the end of the pre-implementation period and a monthly increase in the probability ranged from zero (for element E) to 0.05 (for element D). To be conservative in power calculation, we used a probability of 0.05 for the level and a 0.05 monthly increase in the probability for the slope in the pre-implementation period. Our power analysis suggested that our data will have 80% power to detect an odds ratio (OR) of 1.25 (corresponding to an increase of 0.02 in the probability of receiving bundle performance) and 80% power to detect a slope change, with an OR of 1.52 corresponding to pre- vs. post-difference of 0.03 in the monthly increase of the probability of receiving bundle care. Based on our preliminary data, we reasonably assumed an autocorrelation of 0.5 under the first order auto-regressive covariance structure, a within-patient correlation of 0.5, and a within-hospital correlation of 0.6 in our simulation-based power calculation. Under the same assumptions, we also conducted power analyses on the effects of patient characteristics on the level and slope changes. For patient characteristics with 20:80 distribution, our sample size will have 80% power to detect an OR of 1.73 for the effect of patient characteristics on level change and 80% power to detect an OR of 2.65 for the effect of patient characteristic on slope change. The above power calculation is the most conservative scenario. The study power will be greater than 80% for other cases (e.g., pre-probability of 0.5, patient characteristics with 50:50 distribution). Regardless of study power, we will report point estimates, 95% confidence intervals, and use clinical significance to guide results interpretation. All above calculations were based on multilevel segmented logistic regression with a 0.05 two-sided significance level and adjusted for data dependencies described above.

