Sample Size/Power Analysis. The reliability of ICU-specific performance rates depends on sample size in each hospital (ICU days after adjusting for within-patient clustering). Using the Spearman-Brown prophecy formula,^{138,139} a minimal sample size of 10 is needed to generate reliable ICU-specific estimates (reliability ≥ 0.8), assuming an intraclass correlation of 0.3 for between-ICU variation based on our preliminary analysis. Given the large number of observations in our data ($\sim 49,000$ ICU patient-days nested in $\sim 15,000$ patients in 68 ICUs), there will be sufficient sample size to generate an ICU-specific performance estimate with ≥ 0.8 reliability, even conservatively assuming a large within-patient correlation of 0.8. We conducted power analysis for the effects of organization-level characteristics using the same simulation-based approach described for Aim 1 power analysis. Under the most conservative scenario (see power analysis of Aim 1), our sample size will have sufficient power ($\geq 80\%$) to detect an OR of 1.80 for the effect of an implementation strategy (used vs. not used by the site) on level change and an OR of 2.96 for the effect of an implementation strategy in slope change, assuming 20:80 distribution of the implementation strategy (used vs. not used by the site).

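### Aims 2 and 3 test ICU-level predictors of level and slope change without stating that those changes vary randomly by ICU; if only intercepts vary, the tests are too liberal

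*Combined protocol and SAP*

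**What the plan says.** - **Aim 1, Data analysis.** The segmented logistic model has four coefficients: intercept, pre-period slope, level change and slope change. Each gets fixed effects of patient characteristics plus a patient-specific random effect. Clustering within organizations is mentioned only as a possible extension.
- **Aim 2, Data Analysis.** The strategy is carried over from Aim 1 and ICU-specific random effects are added. Organizational characteristics then enter as fixed effects on level change and slope change. On the error structure the text says: "multilevel clustering (within-patient clustering of ICU days and within-ICU clustering of patients) will be adjusted in the model using random effects terms". ICU variation is summarised by an intraclass correlation.
- **Aim 3, Data Analysis (Survey).** Implementation strategies are handled as organizational characteristics are in Aim 2, as fixed effects on level and slope change, "with patient-, hospital-, and organization-specific random effects to adjust for multilevel clustering effects". ICU is not named in that list.
- **Aim 2, Sample Size/Power Analysis.** With 68 ICUs and a 20:80 split of sites, at least 80% power is claimed for "an OR of 1.80 for the effect of an implementation strategy (used vs. not used by the site) on level change" and for "an OR of 2.96 for the effect of an implementation strategy in slope change". The method is the Aim 1 simulation. Its listed dependence inputs (Aim 1, Power analysis) are an AR(1) autocorrelation of 0.5, a within-patient correlation of 0.5 and a within-hospital correlation of 0.6, "with a 0.05 two-sided significance level".
- **Preliminary Data.** "Bundle performance was highly variable among ICUs and across individual bundle elements".

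**The concern.** A strategy or organizational feature acting on level or slope change is a cross-level interaction: an ICU-level variable times period or time. Its evidence comes from comparing the change in ICUs that have the feature with the change in those that do not, so there are at most 68 replicates however many ICU-days each supplies. The error must include the ICU-to-ICU variation in change. A random intercept removes only stable differences in level.

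Patient-level random effects on the change coefficients cannot fill the gap. Under Aim 1, Procedures and Data Sources, a patient contributes at most seven ICU days, the baseline runs January to June 2015, and implementation starts in January 2016. The period indicator is therefore constant within every patient. Effects that are independent between patients average out over the roughly 224 patients per ICU (15,226/68), whereas a change shared by a whole ICU does not.

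These tests are the main inferential output on organizational features and strategies, and the results are meant to inform a later cluster randomized trial. The Aim 3 survey lists 73 strategies. If each were tested once on one outcome and none had an effect, a 5% test would flag about 3.7 (73 × 0.05) and an 11% test about 8.0 (73 × 0.11).

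**Working it through.** **Inputs from the documents.** 68 ICUs; 20:80 split, taken as 14 and 54; two-sided alpha 0.05; power 80%; site-level ORs 1.80 (level) and 2.96 (slope); patient-level ORs for the same split 1.73 and 2.65. **Assumed.** The between-ICU SD of change, written τ, which the documents do not give.

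**1. The stated figures.** The post-period trajectory and the simulation model are not described, so the pair cannot be reproduced. A generalised least squares (GLS) approximation with τ = 0, ICU intercepts, within-patient correlation 0.5 and no AR(1) term gives a detectable level OR of 1.37 to 2.90, depending on the assumed trajectory and strategy terms. One variant gives 1.82. The slope OR is 1.02 to 1.40 in every variant, never near 2.96. This does not show the stated figures to be wrong. The check below therefore starts from the standard errors they imply:

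- SE₀ = ln(OR)/(1.96 + 0.842)
- Level: ln(1.80)/2.802 = 0.5878/2.802 = 0.210
- Slope: ln(2.96)/2.802 = 0.387

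**2. Adding between-ICU variance of level change.** SE² = SE₀² + τ²(1/14 + 1/54) = 0.0440 + 0.0899τ². Type I error if τ is left out of the model is 2[1 − Φ(1.96 × SE₀/SE)]. Power at 1.80 with τ correctly included is Φ(0.5878/SE − 1.96). The detectable OR is exp(2.802 × SE).

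| τ (log-odds) | SE | Type I error if τ omitted | Power at OR 1.80 | Detectable OR |
|---|---|---|---|---|
| 0 | 0.210 | 5% | 80% | 1.80 |
| 0.3 | 0.228 | 7% | 73% | 1.90 |
| 0.5 | 0.258 | 11% | 63% | 2.06 |
| 0.7 | 0.297 | 17% | 51% | 2.30 |
| 1.0 | 0.366 | 26% | 36% | 2.79 |

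**3. Commoner outcomes.** When the outcome is common, SE₀ is smaller and the omitted term dominates. The GLS approximation gives SE₀ of about 0.113 for an element near 50%. With τ = 0.5, SE = √(0.0128 + 0.0225) = 0.188 and type I error is about 24%. With τ = 1.0 it is about 49%. If strategy terms are also put on the two pre-period coefficients, as Aim 2 does for pre-Collaborative survey data, these become about 14% and 33%.

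**4. Simulation check.** Null datasets (400 per setting; 68 ICUs; baseline rate about 5%) were analysed with ICU intercepts only:

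| SD of level change / slope change per month | Rejection, level | Rejection, slope |
|---|---|---|
| 0 / 0 | 6.5% | 5% |
| 0.3 / 0.03 | 6% | 10% |
| 0.5 / 0.05 | 18% | 23% |
| 0.7 / 0.1 | 23% | 50% |

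Monte Carlo error is about 1 to 2.5 points. Uncorrected cluster-robust tests on the same data still rejected up to about 10%.

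**5. Room left by the stated figures.** Moving a 20:80 predictor from patient to site level raises the level OR only from 1.73 to 1.80. The implied variances are (0.5481/2.802)² = 0.0383 and 0.0440. If the whole difference were between-ICU variance of change, τ = √[(0.0440 − 0.0383)/0.0899], or about 0.25.

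**6. Slope.** With SE₀ = 0.387, a τ of 0.05 to 0.20 per month moves power at 2.96 only from 80% to 79%. The large slope rejection rates in step 4 arise because the slope change there is estimated far more precisely (SE about 0.013) than 2.96 implies.

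**The case against.** The strongest reply is that nothing in the plan restricts the ICU effect to the intercept. Aim 2 says its strategy is that of Aim 1, where all four coefficients are random, and then adds ICU-specific random effects in the plural. It also ranks ICUs on adjusted rates in the last implementation month, a choice that would not matter to the ranking if only intercepts varied. Aim 3 refers back to Aim 2, and the plan elsewhere uses hospital where it means ICU, so the missing word there is minor. All of this stands. A reader might infer that the plan excludes ICU-varying change and that its p-values are therefore invalid; the text does not support that. It leaves the structure unstated, while describing the ICU effects as a clustering adjustment summarised by a single intraclass correlation.

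Three further inferences should also be resisted.

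- **The interquartile ranges above 20% in Preliminary Data do not give τ.** They describe unadjusted rates, and a random intercept absorbs stable differences in level. They make variation in change plausible, because complete performance was below 4% at baseline, but a common log-odds shift would also widen the spread.
- **The power simulation cannot be shown to have omitted this variance.** That is inferred from its listed inputs. The unit of the AR(1) term is not stated, and a zero-τ calculation at a 10% rate gives 1.66 rather than 1.80, a gap equivalent to τ of about 0.35.
- **The 2.96 slope figure is not undermined on this ground** (step 6).

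It is also fair that strategies pass through ratings, concept mapping and an expert panel before they inform a trial. That softens the consequence but does not repair the test.

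**Conclusion.** The point holds as a conditional one. The plan tests ICU-level predictors of level and slope change, states random effects on those coefficients only at patient level, where change cannot be observed, and does not say which coefficients carry the ICU or hospital effects. If they are intercepts only, type I error for level change is close to nominal at a between-ICU SD of 0.3 (about 7%) and material from about 0.5 (11% on the SE implied by 1.80, more for common elements). If 1.80 was computed without this variance, the claimed 80% is about 63% at an SD of 0.5 and 36% at 1.0.

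These sizes rest on assumed SDs, a 14:54 split and a simple additive variance. Inflation of the slope test is less certain in size, because it depends on a slope SE that the plan's own figure does not support. The remedy is cheap and uses data already in hand, so it should be in place before the Aim 2 and Aim 3 models are fitted.

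**What to change.** - In the Data Analysis sections of Aims 2 and 3, state ICU-level random effects for the intercept, level change and slope change, and simplify only if a variance is estimated at zero. Name ICU explicitly in Aim 3.
- Test ICU-level predictors with ICU-level degrees of freedom, counting the ICUs that supply the predictor (68 for the pre-Collaborative organizational survey, 42 for the later one), or with cluster-robust inference that has a small-sample correction.
- In Aim 2, Sample Size/Power Analysis, rerun the level-change simulation over a stated range of between-ICU variance of change estimated from the existing data, and present 1.80 as conditional on that variance. The 2.96 figure needs no restatement for this reason.

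The cost is heavier model fitting with possible convergence work, wider intervals for organizational and strategy effects, and a less favourable detectable OR. No new data are needed.
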